5.2.2 Endoscopy

Endoscopies will be performed for the evaluation of SES-CD and mucosal ulceration at the visits indicated in Flow Chart A

Lesions detected by endoscopy (ileocolonoscopy) will be scored by means of the validated SES-CD, as described below. The same endoscopist at the trial site will complete the SES-CD for each endoscopy immediately after the procedure. The investigator (or designate) will record each endoscopy and send the video to the central imaging laboratory. A central reading of all endoscopies will be performed by an independent blinded reviewer and the findings scored using SES-CD. Eligibility at Screening must be confirmed using the centrally read scores prior to randomization.

BI Trial No.: 1297.4		
c09542349-05 T	rial Protocol Page 44 of	93

The results for SES-CD and mucosal ulceration will be returned to the trial site from the central imaging laboratory for entry into the appropriate eCRF.

5.2.2.1 SES-CD

The SES-CD was developed as a reproducible measure that could be used to assess response to therapy in CD (R14-2969, R15-6247) using an endoscopic index capable of assessing the severity of mucosal lesions in colonic or ileocolonic CD. The scoring system is represented in Table 5.2.2: 1 below. The index is relatively complex and must be performed by an experienced endoscopist who has been trained in the precise and specific data recording procedure required.

Table 5.2.2.1: 1Scoring system for SES-CD

	Ileum	Right colon	Transverse colon	Left colon	Rectum	Total
Presence and size of ulcers (0-3)	0-3	0-3	0-3	0-3	0-3	0-15
Extent of ulcerated surface (0-3)	0-3	0-3	0-3	0-3	0-3	0-15
Extent of affected surface (0-3)	0-3	0-3	0-3	0-3	0-3	0-15
Presence and type of narrowings (0-3)	0-3	0-3	0-3	0-3	0-3	0-11
					SES-CD =	0-56

Source: R14-2969.

Page 45 of 93

Proprietary confidential information © 2017 Boehringer Ingelheim International GmbH or one or more of its affiliated companies

5.3 ASSESSMENT OF SAFETY

5.3.1 Physical examination

A physical examination will be performed at the visits indicated in Flow Chart A and Flow Chart B.

Whenever possible, the same person should perform the physical examination throughout the trial (i.e., for all patients at each trial site). The physical examination will include assessment of general appearance, skin, head, neck, throat, lymph nodes, cardiovascular, and neurological systems, thyroid gland, musculoskeletal system/limbs, respiratory tract, and abdomen. Clinically relevant abnormal findings will be reported as baseline conditions or AEs.

Body weight will also be measured. Height will be measured at Screening only.

5.3.2 Vital Signs

Vital signs will be assessed at the visits indicated in Flow Chart A and Flow Chart B.

Blood pressure and pulse rate measurements should be taken following at least 5 minutes rest while the patient is in a sitting position. The patient's body temperature will also be recorded.

The investigator must assess all vital signs findings at each visit. If the investigator finds any clinically relevant abnormalities, these must be reported as AEs/SAEs as appropriate (see Section 5.3.6).

5.3.3 Safety laboratory parameters

Blood and urine samples for determination of serum chemistry, hematology, urinalysis, and other tests will be taken at the times indicated in Flow Chart A and Flow Chart B.

The laboratory parameters listed in Appendix 10.2 will be measured.

The investigator must assess all laboratory results. The investigator will evaluate any change in laboratory values and all clinical laboratory tests will be reviewed for potential clinical significance at all time points throughout the trial. The investigator should endeavor to provide a reason for all results deemed not clinically significant. If the investigator

Boehringer Ingelheim		12 Dec 2017
BI Trial No.: 1297.4		
c09542349-05	Trial Protocol	Page 46 of 93

determines a laboratory abnormality to be clinically significant, it will be considered an AE/SAE (see Section 5.3.6); however, if the laboratory value abnormality is consistent with a current diagnosis, it will be documented accordingly.

Blood and stool samples will be analyzed by a central laboratory. The central laboratory vendor will also provide the materials for blood sampling. Instructions for the labeling, storage, and shipment of the samples can be found in the Laboratory Manual. Details of all blood variable units, reference ranges, and blood sample volumes can be found in the Laboratory Manual.

At Week 4, in order to assess clinical response during the visit, the hematocrit value required to determine CDAI score will be assessed locally and subsequently confirmed via central laboratory assessment.

Pregnancy testing will be performed by a central laboratory using serum at Screening or by a local laboratory using urine at all applicable visits thereafter.

It should also be noted that additional samples may be required if medically indicated, e.g., at unscheduled visits to follow safety findings.

5.3.4 Electrocardiogram

A 12-lead ECG (I, II, III, aVR, aVL, aVF, V1 – V6) will be recorded using a computerized electrocardiograph at the visits indicated in Flow Chart A and Flow Chart B.

All ECGs will be recorded for 10-second duration after the patients have rested for at least 5 minutes in a supine position. ECG assessment will always precede all other trial procedures at the same time point (except blood drawing from an i.v. cannula which is already in place) to avoid impact of sampling on the ECG quality.

The electronic version of the ECG is regarded as source data. Dated and signed printouts will be stored in the patient's medical file.

The investigator or a designate will evaluate whether the ECG is normal or abnormal and whether it is clinically significant, if abnormal. Additionally, any occurrence of re- or depolarization disorders, arrhythmic disorders or other abnormalities will be assessed. ECGs may be repeated for quality reasons (like alternating current artefacts, muscle movements, electrode dislocation) and the repeated ECG will be used for analysis. Additional (unscheduled) ECGs may be collected by the investigator for safety reasons.

Abnormal findings will be reported as AEs (during the trial) or baseline conditions (at Screening) if judged clinically relevant by the investigator. Any ECG abnormalities, judged as clinically relevant, will be monitored carefully and, if necessary, the patient will be removed from the trial and will receive the appropriate medical treatment. Additionally, evaluation of these ECGs will be performed by a board certified cardiologist.

Information about the details of ECG collection and the parameters assessed will be provided in the ISF.

Page 47 of 93

Proprietary confidential information © 2017 Boehringer Ingelheim International GmbH or one or more of its affiliated companies

5.3.5 Other safety parameters

5.3.5.1 Tuberculosis assessment

A chest X-ray will be reviewed by the investigator or designee at Screening. If chest radiographs have been taken within 12 weeks of the Screening Visit then the chest radiographs do not need to be repeated (as long as they show no clinically significant abnormality and no signs or symptoms suggestive of lung disease that would exclude the patient from the trial). The results must be entered into the eCRF.

An IGRA (e.g., QuantiFERON[®]-TB Gold) will be used to assess TB status at Screening and, for patients who continue to the maintenance phase, at Visit 14 Week 24 (before switch from EU-approved Humira to BI 69550 and at EoT (Week 48 or earlier for patients who discontinued treatment during the maintenance phase). In the event of an indeterminate result at Screening, the test should be repeated. If a second indeterminate result is obtained then the patient must be excluded from the trial participation.

In the event of an indeterminate or positive result during the study, the test should be repeated and if a result is positive, then the patient will discontinue receiving the study treatment and followed up for safety. The patient will be referred to the specialist as required by local regulations.

5.3.6 Assessment of adverse events

5.3.6.1 Definitions of AEs

Adverse event

An AE is defined as any untoward medical occurrence in a patient or clinical investigation subject administered a medicinal product and which does not necessarily have to have a causal relationship with this treatment.

An AE can therefore be any unfavorable and unintended sign (including an abnormal laboratory finding), symptom, or disease temporally associated with the use of a medicinal product, whether or not considered related to the medicinal product.

Adverse reaction

An adverse reaction is defined as a response to a medicinal product which is noxious and unintended. Response in this context means that a causal relationship between a medicinal product and an AE is at least a reasonable possibility. Adverse reactions may arise from use of the product within or outside the terms of the marketing authorization or from occupational exposure. Conditions of use outside the marketing authorization include off-label use, overdose, misuse, abuse, and medication errors.

Serious adverse event

Page 48 of 93

Proprietary confidential information © 2017 Boehringer Ingelheim International GmbH or one or more of its affiliated companies

An SAE is defined as any AE which:

- results in death,
- is life-threatening, referring to an event in which the patient is at risk of death at the time of the event; it does not refer to an event that hypothetically might cause death if more severe,
- requires inpatient hospitalization or
- prolongation of existing hospitalization,
- results in persistent or significant disability or incapacity, or
- is a congenital anomaly / birth defect, or
- is deemed serious for any other reason if it is an important medical event when based upon appropriate medical judgment which may jeopardize the patient and may require medical or surgical intervention to prevent one of the other outcomes listed in the above definitions.

Medical and scientific judgement should be exercised in deciding whether other situations should be considered serious reactions, such as important medical events that might not be immediately life threatening or result in death or hospitalization but might jeopardize the patient or might require intervention to prevent one of the other outcomes listed above. Examples of such events are intensive treatment in an emergency room or at home for allergic bronchospasm, blood dyscrasias, or convulsions that do not result in hospitalization, or development of dependency or abuse. Any suspected transmission via a medicinal product of an infectious agent is also considered a serious adverse reaction.

AEs considered "Always Serious"

Cancers of new histology and exacerbations of existing cancer must be reported as a serious event regardless of the duration between discontinuation of the drug and the occurrence of the cancer.

In accordance with the European Medicines Agency initiative on Important Medical Events, Boehringer Ingelheim has set up a list of further AEs, which by their nature, can always be considered to be "serious" even though they may not have met the criteria of an SAE as given above.

The latest list of "Always Serious AEs" will be provided in the ISF. These events should always be reported as SAEs as described above.

Adverse events of special interest (AESIs)

The term AESI relates to any specific AE that has been identified at the project level as being of particular concern for prospective safety monitoring and safety assessment within this trial, e.g., the potential for AEs based on knowledge from other compounds in the same class. AESIs need to be reported to the sponsor's Pharmacovigilance Department within the same timeframe that applies to SAEs (see above).

Page 49 of 93

Proprietary confidential information © 2017 Boehringer Ingelheim International GmbH or one or more of its affiliated companies

The following are considered as AESIs:

• Hepatic injury

A hepatic injury is defined by the following alterations of hepatic laboratory parameters:

- an elevation of AST and/or ALT ≥3 fold ULN combined with an elevation of total bilirubin ≥2 fold ULN measured in the same blood draw sample, and/or
- marked peak aminotransferase (ALT and/or AST) elevations ≥ 10 fold ULN

These laboratory findings constitute a hepatic injury alert and the patients showing these laboratory abnormalities need to be followed up according to the "DILI checklist" provided in the ISF.

In case of clinical symptoms of hepatic injury (icterus, unexplained encephalopathy, unexplained coagulopathy, right upper quadrant abdominal pain, etc.) without laboratory results (ALT, AST, total bilirubin) available, the investigator should make sure these parameters are analyzed, if necessary in an unscheduled blood test. Should the results meet the criteria of hepatic injury alert, the procedures described in the DILI checklist should be followed.

For further details see Appendix 10.4.

- Anaphylactic reactions
- Serious infection (defined as infections requiring i.v. antibiotics or meeting the regulatory definition of an SAE)
- Hypersensitivity reactions.

Protocol-specified AESIs can be classified as serious or non-serious but all AESIs must be reported in an expedited manner similar to SAEs on an SAE form (i.e., non-serious AESIs must be reported on the SAE form and follow SAE reporting timelines).

Intensity of AEs

The intensity of the AE should be judged based on the following:

Mild:	Awareness of sign(s) or symptom(s) that is/are easily tolerated
Moderate:	Enough discomfort to cause interference with usual activity
Severe:	Incapacitating or causing inability to work or to perform usual activities

Causal relationship of AEs

The definition of an adverse reaction implies at least a reasonable possibility of a causal relationship between a suspected medicinal product and an AE. An adverse reaction, in contrast to an AE, is characterized by the fact that a causal relationship between a medicinal product and an occurrence is suspected.

Medical judgment should be used to determine the relationship, considering all relevant factors, including pattern of reaction, temporal relationship, de-challenge or re-challenge, confounding factors such as concomitant medication, concomitant diseases, and relevant history.

Arguments that may suggest that there is a reasonable possibility of a causal relationship could be:

- The event is consistent with the known pharmacology of the drug
- The event is known to be caused by or attributed to the drug class
- A plausible time to onset of the event relative to the time of drug exposure
- Evidence that the event is reproducible when the drug is re-introduced
- No medically sound alternative etiologies that could explain the event (e.g., pre-existing or concomitant diseases, or co-medications)
- The event is typically drug-related and infrequent in the general population not exposed to drugs (e.g., Stevens-Johnson syndrome)
- An indication of dose-response (i.e., greater effect size if the dose is increased, smaller effect size if dose is diminished).

Arguments that may suggest that there is no reasonable possibility of a causal relationship could be:

- No plausible time to onset of the event relative to the time of drug exposure is evident (e.g., pre-treatment cases, diagnosis of cancer or chronic disease within days/weeks of drug administration; an allergic reaction weeks after discontinuation of the drug concerned)
- Continuation of the event despite the withdrawal of the medication, taking into account the pharmacological properties of the compound (e.g., after 5 half-lives). Of note, this criterion may not be applicable to events whose time course is prolonged despite removing the original trigger.
- Additional arguments amongst those stated before, like alternative explanation (e.g., situations where other drugs or underlying diseases appear to provide a more likely explanation for the observed event than the drug concerned)
- Disappearance of the event even though the trial drug treatment continues or remains unchanged.

5.3.6.2 Adverse event collection and reporting

AE Collection

The investigator shall maintain and keep detailed records of all AEs in their patient files.

[figure not shown]
The following must be collected and documented on the appropriate eCRF(s) by the investigator:

- From signing the informed consent onwards through the REP (defined as 10 weeks after last administration of trial medication), until the individual patient's end of trial:
 - All AEs (serious and non-serious) and all AESIs

However, if an individual patient discontinues trial medication prematurely but stays in the trial (i.e., if further visits incl. telephone visits, or vital status assessments are planned) from then on and until the individual patient's end of the trial, the investigator must report related SAEs and related AESIs.

- After the individual patient's end of trial:
 - The investigator does not need to actively monitor the patient for AEs but should only report relevant SAEs and relevant AESIs of which the investigator may become aware.

The above instructions are summarized schematically below.

The REP is defined as 10 weeks after the last trial medication application. All AEs which occurred through the treatment phase and throughout the REP will be considered as on treatment (see Section 7.3.4). Events which occurred after the REP will be considered as post-treatment events.

AE reporting to sponsor and timelines

The investigator must report SAEs, AESIs, and non-serious AEs which are relevant for the reported SAE or AESI, on the BI SAE form via fax immediately (within 24 hours) to the sponsor's/sponsor's designee's unique entry point (specific contact details will be provided in the ISF). The same timeline applies if follow-up information becomes available. In specific occasions the investigator could inform the sponsor/sponsor's designee upfront via telephone. This does not replace the requirement to complete and fax the BI SAE form.

Page 52 of 93

Proprietary confidential information © 2017 Boehringer Ingelheim International GmbH or one or more of its affiliated companies

With receipt of any further information to these events, a follow-up SAE form has to be provided. For follow-up information the same rules and timeline apply as for initial information.

Information required

For each AE, the investigator should provide the information requested on the appropriate eCRF pages and the BI SAE form. The investigator should determine the causal relationship to the trial medication and any possible interactions between the investigational drug(s) and a non-investigational medicinal product/auxiliary medicinal product.

The following should also be recorded as an (S)AE in the eCRF and SAE form (if applicable):

- Worsening of the underlying disease or of other pre-existing conditions
- Changes in vital signs, ECG, physical examination, and laboratory test results, if they are judged clinically relevant by the investigator.

If such abnormalities already pre-exist prior trial inclusion they will be considered as baseline conditions.

All (S)AEs, including those persisting after individual patient's end of trial must be followed up until they have resolved, have been sufficiently characterized, or no further information can be obtained.

Pregnancy

In rare cases pregnancy may occur in a clinical trial. Once a patient has been enrolled into this clinical trial and has taken trial medication, the investigator must report immediately (within 24 hours) a potential drug exposure during pregnancy (DEDP) to the sponsor's/sponsor's designee's unique entry point (specific contact details will be provided in the ISF). The Pregnancy Monitoring Form for Clinical Trials (Part A) should be used.

The outcome of the pregnancy associated with the drug exposure during pregnancy must be followed up and reported to the sponsor's/sponsor's designee's unique entry point on the Pregnancy Monitoring Form for Clinical Trials (Part B).

The ISF will contain the Pregnancy Monitoring Form for Clinical Trials (Part A and B).

As pregnancy itself is not to be reported as an AE, in the absence of an accompanying SAE and/or AESI, only the Pregnancy Monitoring Form for Clinical Trials and not the SAE form is to be completed. If there is an SAE and/or AESI associated with the pregnancy an SAE form must be completed in addition.

09542349-05Trial ProtocolPage 53 of 93Proprietary confidential information © 2017 Boehringer Ingelheim International GmbH or one or more of its affiliated companies

09542349-05Trial ProtocolPage 54 of 93Proprietary confidential information © 2017 Boehringer Ingelheim International GmbH or one or more of its affiliated companies

Page 55 of 93

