- ⁸ Findings of ALT or AST >1.5 times the ULN or hemoglobin <8.0 g/dL at Screening are criteria for exclusion.
- ⁹ Adverse events will be collected from the time of informed consent. Adverse events continuing at the EoT Visit must be followed to resolution or follow-up as agreed by the investigator and medical monitor. For patients who complete the trial or who discontinue the trial early, new AEs will be captured until the end of the 10-week safety follow-up period.
- ¹⁰ CDAI determination: where applicable, exclude the day of bowel preparation for colonoscopy due to misleading impact on assessment of pain and liquid stool frequency. The CDAI evaluation at Visit 1.1 will be performed based on the CDAI diary provided to the patient at Visit 1 (a minimum of 7 days must be allowed between visits for completion of the diary). For subsequent CDAI evaluations, the diary will be provided to the patient at the previous planned visit. At Visit 4 (Week 4), the hematocrit value to determine CDAI score will be assessed locally and confirmed via central laboratory assessment. At visits where no physical examination is performed, weight must be measured for use in CDAI determination.

¹² IRT will be contacted prior to every trial medication administration visit.

¹³ Contact IRT to confirm whether or not patient has achieved a clinical response (CDAI decrease ≥70). Patients who are non-responders will have an EoT visit and every effort should be made to ensure that they return for a Safety Follow-up visit 10 weeks after their last dose of trial medication. Patients achieving a clinical response at Week 4 will be eligible to continue in the trial (maintenance period) as shown in Flow Chart B.

¹⁴ Trial medication should be administered every 2 weeks (±1 day up to Visit 4). Patients will receive each dose of trial medication at the trial site until Week 22, trial medication will be administered by suitably qualified, designated unblinded trial personnel (Third party blinding). All assessments and procedures should be performed prior to trial medication administration, unless otherwise stated.

Page 10 of 93

Proprietary confidential information © 2017 Boehringer Ingelheim International GmbH or one or more of its affiliated companies

FLOW CHART B: MAINTENANCE PERIOD

Visit	4 ¹	5	6	7	8	9	10	11	12	13
Week	4	6	8	10	12	14	16	18	20	22
Day	29	43	57	71	85	99	113	127	141	155
Permitted visit window (days)	±1	±3	±3	±3	±3	±3	±3	±3	±3	±3
LABS/SAFETY ASSESSMENTS										

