7.3.4 Safety analyses

Adverse events will be coded using the MedDRA coding dictionary.

Boehringer Ingelheim		12 Dec 2017
BI Trial No.: 1297.4		
c09542349-05	Trial Protocol	Page 65 of 93

All treated patients will be included in the safety analysis. In general, safety analyses will be descriptive in nature. No hypothesis testing is planned. No formal inferential analyses are planned for safety comparison. The analyses will be based on the SAF.

Statistical analysis and reporting of AEs will concentrate on treatment-emergent AEs. To this end, all AEs occurring between start of treatment and end of the REP will be considered 'treatment-emergent'. The REP is defined as 10 weeks after the last dose of trial medication. Adverse events that start before first drug intake and deteriorate under treatment will also be considered as 'treatment-emergent'. Other AEs will be assigned to the appropriate trial phases, i.e., screening or post-treatment. For patients switching from EU-approved Humira to BI 695501, AEs occurring after the first dose of BI 695501 will be assigned to BI 695501 for the overall AE analysis. AEs occurring before the first dose of BI 695501 will be assigned to the ongoing treatment.

Frequency, severity, and causal relationship of AEs will be tabulated by system organ class and preferred term after coding according to the current version of MedDRA. In addition, RR and risk difference together with 95% CIs will be presented for the overall population (details will be specified in the TSAP).

Laboratory data will be analyzed quantitatively as well as qualitatively. The latter will be done via comparison of laboratory data with their reference ranges. Values outside the reference range as well as values defined as clinically relevant will be highlighted in the listings. Treatment groups will be compared descriptively with regard to distribution parameters as well as with regard to frequency and percentage of patients with abnormal values or clinically relevant abnormal values.

Vital signs, physical examinations, or other safety-relevant data observed at screening, baseline, during the course of the trial and at the end-of-trial evaluation will be assessed with regard to possible changes compared with findings before start of treatment.

Page 66 of 93

Proprietary confidential information © 2017 Boehringer Ingelheim International GmbH or one or more of its affiliated companies

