16.1.7.6. Anaphylactic reactions

Anaphylactic reactions are those events recorded as MedDRA code in the pre-defined Standardized MedDRA Queries (SMQ) = "Anaphylactic reactions" (narrow)

Anaphylactic reaction adverse events of special interest (Anaphylactic reaction AESI) are those events both identified as Anaphylactic reactions and recorded as "Adverse Event of Special Interest" equal to "Yes" on the Adverse Events page of the eCRF.

Anaphylactic reactions will also be listed. The listing will include the "Adverse Event of Special Interest" equal to "Yes" information from the Adverse Events page of the eCRF as a flag.

16.1.8. AEs OCCURRING AFTER THE LAST INJECTION FOR SUBJECTS DISCONTINUED DUE TO LACK OF EFFICACY

Subjects who discontinued treatment due to lack of efficacy will be identified from "End of treatment visit" eCRF page, where "Reason for End of Treatment" is "Progressive Disease".

Number of subjects, percentages, and number of events occurring after the last injection and prior to the last injection + 10 weeks for subjects discontinued due to lack of efficacy by SOC and PT will be prepared.

AEs occurring after the last injection and prior to the last injection + 10 weeks for subjects discontinued due to lack of efficacy will be listed.

Document: \\ieedc-vnasc01\BIOSdata\Boehringer_Ingelheim\BI_695501\NVA96252\Biostatistics\Documentation\SAP\BI1297.4 SAP FINAL v4.0_22MAY2019.docx

Author: Version Number: Final V4.0
Version Date: 22MAY2019

Template No: CS_TP_BS016 Revision 5 Reference: CS_WI_BS005
Effective Date: 01Apr2018

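### Protocol 5.3.6.2, as most naturally read, cuts AE reporting at early discontinuation, while the flow charts, Protocol 7.3.4 and the SAP need all AEs to 70 days after the last dose

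*Protocol*

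**What the plan says.** **Protocol 5.3.6.2 (AE Collection).** From consent through the REP, investigators document on the eCRF "All AEs (serious and non-serious) and all AESIs". The REP is 10 weeks after the last administration. The next sentence opens with 'However' and applies "if an individual patient discontinues trial medication prematurely but stays in the trial", meaning that further visits, telephone contacts or vital-status checks are planned. From then until that patient's end of trial, "the investigator must report related SAEs and related AESIs". Later in the same section: "All AEs which occurred through the treatment phase and throughout the REP will be considered as on treatment".

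**Flow Chart A footnote 9 and Flow Chart B footnote 5.** For patients who complete, and for those "who discontinue the trial early, new AEs will be captured until the end of the 10-week safety follow-up period".

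**Protocol 7.3.4.** Every AE from the start of treatment to the end of the REP is treatment-emergent.

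**SAP 16.1.1.1.** The window for a treatment-emergent AE (TEAE) closes 70 days after the last dose. Both period definitions say so expressly for patients who stop treatment early.

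**SAP 16.1.8.** A table and a listing are planned of "AEs occurring after the last injection and prior to the last injection + 10 weeks for subjects discontinued due to lack of efficacy".

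**The concern.** The analysis window and the collection rule do not match for patients who stop early. The analysis counts any AE up to 70 days after the last dose. The collection rule, in the section written to govern collection, appears to narrow at the moment medication stops.

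Three kinds of event could then go unrecorded although they count as treatment-emergent:
- non-serious events that are not AESIs;
- SAEs judged unrelated;
- AESIs judged unrelated.

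This touches the secondary safety endpoints. Protocol 5.1.2 lists the proportions of patients with any AE, with infections and with injection-site reactions. Protocol 7.3.2.2 attaches a risk ratio and a risk difference with 95% CIs to them. In the SAP 16.1.7 allocation table, infections that are not serious and injection-site reactions are not AESIs, so the sentence would not require them.

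Sites that follow the flow charts would collect everything. Sites that follow 5.3.6.2 would not. Ascertainment could therefore vary by site as well as by discontinuation status.

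**Working it through.** No planned statistical figure is in dispute, so there is none to reproduce. The check is a comparison of the texts, followed by a count of the patients potentially affected.

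**1. When does the reduced rule start?** The trigger is stopping medication, and the duration is from then on. The sentence does not mention the REP. The all-AE rule just before it runs through the REP. For a discontinuer still inside the REP, the two give different instructions.

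**2. Does the sentence reduce anything?** It follows an all-AE rule and opens with 'However'. If all AEs were still to be recorded, it would add nothing during the REP. The natural reading is therefore a reduction.

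**3. What do the other sections need?**

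| Source | AEs after early stop, within 10 weeks of last dose |
|---|---|
| Protocol 5.3.6.2, contrasting sentence | related SAEs and related AESIs |
| Flow Chart A fn 9, Flow Chart B fn 5 | all new AEs |
| Protocol 7.3.4 | all count as treatment-emergent |
| SAP 16.1.1.1 | all count as TEAEs, to 70 days |
| SAP 16.1.8 | all tabulated and listed for lack-of-efficacy discontinuers |

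**4. Who can fall under the sentence?** Protocol 3.3.4.1 lists absence of a Week 4 response as a reason for discontinuing treatment. Flow Chart A footnote 2 plans a Safety Follow-up visit 10 weeks after the last dose for those who discontinue. A non-responder with that visit planned can meet the condition.

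**5. How many?** Week 4 non-responders = N × (1 − response rate), with N = 130 (Protocol 7.7).
- Assumed response of 80% (Protocol 7.7): 130 × 0.20 = 26 (20%).
- Historical pooled 54.1% (Protocol Appendix 10.3): 130 × 0.459 = 59.7, about 60 (46%).
- Over its 95% CI, 60.4% to 47.6%: 130 × 0.396 = 51.5 and 130 × 0.524 = 68.1, about 51 to 68.

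Later discontinuations would add to these.

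**6. How much of the window?** Protocol 4.1.4 describes a Week 4 injection for each patient and also says that non-responders receive no further treatment, so I show both cases. If the last injection was on Day 15, stopping on Day 29 leaves 70 − (29 − 15) = 56 of 70 days under the reduced rule. If it was on Day 29, all 70 days fall under it.

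**The case against.** The strongest reply is that the sentence was meant for the time after the REP. Protocol 3.3.4.1 asks for early discontinuers to be followed for efficacy at Week 48, which can be long after their REP ends. Reduced reporting would be sensible then, and it would fit the mention of telephone visits and vital status. It would also fit the statement in the same section that AEs throughout the REP are on treatment. This is plausible as intent, but the text starts the rule at discontinuation, so the wording still needs repair.

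Other points carry weight:
- The sentence does not contain the word 'only', although the bullet on events after the end of trial does. The restriction is an inference, if the natural one.
- The section refers to a schematic that is not available here. It might show when reduced reporting begins.
- The flow charts mark AEs at the End of Treatment and Safety Follow-up visits, Protocol 6.2.2 and 6.2.3 list AE assessment there, and Protocol 2.3 describes monitoring to 10 weeks after the last dose. A site would have to put one sentence above all of these to lose data.
- The footnotes speak of discontinuing the trial, the sentence of discontinuing medication. The two might be different groups. Protocol 3.3.4.1 uses the terms almost interchangeably, however, and Protocol 7.3.4 and the SAP define their window by the last dose, so the conflict with them remains.

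A reader might also infer more than the documents support:
- *Every Week 4 non-responder is covered.* The notes to Figure 3.1:1 say that only responders continue in the trial, so whether non-responders stay in it is arguable.
- *The SAP 16.1.8 table would be largely empty.* Related SAEs and AESIs are still reported. Any events between the last injection and the Week 4 decision precede the reduced rule, and sites following the flow charts would supply the rest.
- *The between-arm safety comparison is biased.* The rule is the same in both blinded arms, and the sample size section assumes equal response. Differential loss needs discontinuation or non-response to differ by arm, which nothing in the documents predicts.

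**Conclusion.** The inconsistency is real: Protocol 5.3.6.2 conflicts with itself, with the flow-chart footnotes, with Protocol 7.3.4 and with SAP 16.1.1.1 and 16.1.8. Where a site follows the contrasting sentence as written, non-serious and unrelated TEAEs after discontinuation would be under-recorded, and the SAP 16.1.8 output would be incomplete.

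From Week 4 non-response alone, the group potentially affected is about 26 of 130 patients at the planning rate and about 60 at the historical rate. This assumes that non-responders with a planned Safety Follow-up visit count as staying in the trial. The number of events lost cannot be derived from the documents, because it depends on how sites read the text.

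Confidence is moderate, given the missing schematic and the plausible post-REP intent. The point should be corrected, because it concerns a stated collection rule that feeds the secondary safety endpoints.

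**What to change.** Reconcile the passages by rewording the contrasting sentence in Protocol 5.3.6.2 to say that:
- all AEs and all AESIs are recorded to the end of the REP (last dose + 70 days) for every patient, including those who stop medication early;
- reporting limited to related SAEs and related AESIs applies only after the REP, to patients still being followed.

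Check that the schematic in that section shows the same rule. Send sites a short memo. It can ask them to complete the eCRF from source for patients who have already discontinued, since the section requires detailed records of all AEs in the patient files.

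No change to the SAP definitions is needed. The cost is one protocol sentence, one memo and slightly more AE data entry. No visits are added, because AE assessment is already scheduled at End of Treatment and Safety Follow-up.
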